#### 17.4.2.6.2 Analysis

The number of exacerbations during the first 15 months follow-up will be summarised with median and interquartile range for each treatment arm. A Mann-Whitney U-test will test whether the distribution of number of exacerbations is the same in each treatment arm. The number and percentage of patients experiencing at least one exacerbation in each treatment arm will also be reported. Treatment groups will be compared using the chi-squared test. The Fisher's exact test may be used if the chi-squared test is not appropriate (counts of <5 within categories).

Page 32 of 47

#### 17.4.2.7 Admission to hospital

#### 17.4.2.7.1 Derivation

Each follow-up visit CRF (scheduled and unscheduled) records whether the participant has had any inpatient stays since the last visit. At least one admission to hospital since last follow-up visit is recorded if FUINPTVC='Yes' for scheduled visits, and with UVINPTVC='Yes' for unscheduled visits.

Admission to hospital is split into admission to hospital during three discrete time-periods of interest:

- A: During treatment phase (Baseline to T3)
- B: 12 months post treatment phase ( $T_3$  to  $T_{15}$ )
- C: During the remainder of follow-up ( $T_{15}$  to  $T_{24}$ ) [where applicable]

There are therefore three admission to hospital outcomes  $Y_A$ ,  $Y_B$ , and  $Y_C$ .

Define  $Y_A$ ,  $Y_B$ , and  $Y_C$ :

- YA: There was at least one hospital admission during the treatment phase (not including any relating to IV treatment if in Arm A of trial) (T0-T3)
- (2) YB: There was at least one hospital admission during the first 12 months of follow-up (T3-T15)
- (3) Yc: There was at least one hospital admission during the remainder of follow-up (T15-T24) [where applicable]

As long as scheduled visits occur at  $T_3$  and  $T_{15}$  (and if applicable  $T_{24}$ ) the following table gives the derivation for each outcome:

Outcome	Success criteria	Failure criteria	Assumption
Y A	At least one CRF dated at $T_3$ or earlier reports a hospital admission	No CRFs dated at $T_3$ or earlier report hospital admission	Scheduled visit at T 3 took place
Y B	At least one CRF dated after $T_3$ and at or before $T_{15}$ reports a hospital admission	No CRFs dated after $T_3$ and at or before $T_{15}$ report hospital admission	Scheduled visits at $T_3$ and $T_{15}$ took place
Yc	At least one CRF dated after $T_{15}$ and at or before $T_{24}$ reports a hospital admission	No CRFs dated after $T_{15}$ and at or before $T_{24}$ report hospital admission	Scheduled visits at $T_{15}$ and $T_{24}$ took place

#### Uncertainty regarding time-period that hospital visit occurred in

Where any of the key scheduled visits are missing  $(T_3, T_{15})$ , the next available unscheduled/scheduled visit will act as proxy for the missing visit. However, as dates are not provided for when hospital stays take place, there is uncertainty as to which period of interest to assign reported hospital stay. For the purpose of this analysis, we will assume that all reported hospital stay occurs in the period of interest **most** likely.

Example: an unscheduled visit takes place at 3.5 months reporting inpatient stay. No scheduled visit took place at 3 months. The patient's previous visit took place at 2 months. It is therefore uncertain whether some or all of the reported hospital stay took place during the treatment phase, or in the first 12 months after treatment. The 3.5 month visit data relates to a 1.5 month period, and >50% of this is during the treatment phase. Therefore we will say that the hospital stay is more likely to have occurred in the treatment phase.

#### 17.4.2.7.2 Analysis

The number and percentage of participants having had at least one hospital stay during the first 3 months of treatment, and during the first year after treatment will be reported. The number and percentage of participants who had at least one hospital stay after  $T_{15}$  will also be reported – the denominator will be the number of patients within each treatment arm that were followed up until  $T_{24}$ .

The relative risk with 95% CI of experiencing at least one hospital stay during each time-period of interest will be presented. A chi-squared test will be used to calculate a p-value for this relative risk. Note that if hospital stays are rare, a Fisher's exact test may be needed to calculate the p-value, or it may be the case that no test is possible.

#### Sensitivity analysis:

The analysis will be re-run under the assumption that where there is uncertainty about which period hospital stay occurred in, all reported hospital stay occurs in the time-period **least** likely. The results of both analyses will be compared. If the results lead to different conclusions, the limitations of the data collection methodology should be highlighted in any reporting of this outcome.

# 17.4.2.8 Number of days spent as an inpatient in hospital during treatment phase and between three and fifteen months after randomisation.

#### 17.4.2.8.1 Derivation

Each follow-up visit CRF (scheduled and unscheduled) records the number of days the participant has had any inpatient stays since their last visit. Length of time hospitalised since last follow-up visit is recorded in FUINPTWI and FUINPTDI for scheduled visits and UVINPTWI) and UVINPTVI for an unscheduled visit.

Length of time hospitalised is split by three discrete time-periods of interest:

- A: During treatment phase (Baseline to T3)
- B: 12 months post treatment phase (T3 to T15)
- C: during the remainder of follow-up [if applicable]

There are therefore three length-of-time hospitalised outcomes  $Y_A$ ,  $Y_B$ , and  $Y_C$ .

Define  $Y_A$ ,  $Y_B$ , and  $Y_C$ :

- YA: Number of days hospitalised during the treatment phase (not including any relating to IV treatment if in Arm A of trial) (T0-T3)
- (2) **Y**B: Number of days hospitalised during the first 12 months of follow-up ( $T_3$ - $T_{15}$ )
- (3)  $Y_c$ : Number of days hospitalised during remainder of follow-up ( $T_{15}-T_{24}$ ) [if applicable]

As long as scheduled visits occur at  $T_3$  and  $T_{15}$  [and if applicable  $T_{24}$ ] the following table gives the derivation for each outcome:

Outcome	Derivation	Assumption
Y A	Sum of all weeks and days hospitalised from CRFs dated at $T_3$ or earlier, expressed in days	Scheduled visit at $T_3$ took place
Y B	Sum of all weeks and days hospitalised from CRFs dated after $T_3$ and at or before $T_{15}$ , expressed in days	Scheduled visits at $T_3$ and $T_{15}$ took place
Yc	Sum of all weeks and days hospitalised from CRFs dated after $T_{15}$ and at or before $T_{24}$ , expressed in days	Scheduled visits at $T_{15}$ and $T_{24}$ took place

<sup>3 Protocol wording for this outcome is: "Number of days spent as inpatient in hospital over the threemonth period after allocated treatment has finished, treatment and between three months and 15 months after eradication treatment has finished-finished (other than 14 days spent on initial IV treatment)". Changed above to aid clarity.

It is possible that some CRF data will span two time-periods due to follow-up visits taking place outside of the per-protocol specified window. In these cases, linear interpolation will be used to estimate the total number of days spent in each time-period. This estimate will be added to the known total number of days from the forms that do not incur uncertainty, to get a total for each time-period.

Example: an unscheduled visit takes place at 3.5 months reporting 5 days of inpatient stay. No scheduled visit took place at 3 months. The patient's previous visit took place at 2 months, where 2 days hospitalisation were recorded. It is therefore uncertain whether some or all of the reported hospital stay reported at 3.5 months took place during the treatment phase, or in the first 12 months after treatment. The 3.5 month visit data relates to a 1.5 month period. Therefore on average, one day of hospital stay took place every 0.3 months. So we interpolate that 3.3 visits took place during the treatment phase, and 1.7 took place during the first 0.5 months of follow-up. Adding to the data from the 2-month visit, we have an estimated total of 5.3 days stay for the treatment phase.

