#### 8.9 Schedule of assessments

Table 3 in Section 7 of the protocol outlines the schedule of assessments.

Note that for the purpose of this trial, a 'month' is defined as 28 days. Visits should have occurred as follows:

	Scheduled study visit	Time after treatment start
T 3	3 months	12 weeks
$T_6$	6 months	24 weeks
T 9	9 months	36 weeks
T 12	12 months	48 weeks
T 15	15 months	60 weeks
T 18	18 months	72 weeks
T 21	21 months	84 weeks
T 24	24 months	96 weeks

Due to large numbers of visits occurring outside of appropriate visit windows and not consistently being captured on scheduled or unscheduled visit CRFs; where outcomes refer to specific time points, data will be included based on dates of assessments rather than CRF names. For an assessment to be associated with a particular time-point it must have occurred within 1 week either side of the expected visit date, apart from  $T_{15}$  which may be minus 1 week or plus 2 weeks of the expected visit date.

Not all patients were followed up after  $T_{15}$ .  $T_{18}$ ,  $T_{21}$  and  $T_{24}$  were proposed in the protocol up to and including version 7. Patients randomised after 1st January 2016 were required to complete up to and including  $T_{15}$  only.

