#### 17.4.2.8.2 Analysis

The number of patients with hospital stays and their median, interquartile range and minimum and maximum total length of stay will be calculated for each treatment arm and each timeperiod. A Mann-Whitney test will be used to detect differences between treatment groups for each time-period of interest.

Two sensitivity analyses will be carried out: in each case where linear interpolation is needed (1) assume that all time spent hospitalised refers to the most probable time-period (so in the example assume that all 5 days recorded at 3.5 month visit occurred in the treatment phase; (2) assume that all time spent hospitalised refers to the least probable time-period (so in the example assume that all 5 days recorded at 3.5 month visit occurred during follow-up.

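### The rules for follow-up forms that span T3 do not remove Arm A's initial IV hospital stay first, so read literally they count some or all of it in T3–T15

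*SAP*

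**What the plan says.** Two secondary outcomes are involved: any hospital admission (SAP 17.4.2.7) and number of inpatient days (SAP 17.4.2.8). Each is divided into Y_A (baseline to T3), Y_B (T3 to T15) and Y_C (after T15).

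- **Source.** For the days outcome, each follow-up form "records the number of days the participant has had any inpatient stays since their last visit". A stay on a form that crosses a boundary cannot be placed, "as dates are not provided for when hospital stays take place" (17.4.2.7).
- **Exclusion.** In both sections Y_A carries the qualifier "not including any relating to IV treatment if in Arm A of trial". Y_B carries none, and the derivation tables add up whatever the forms in the period report.
- **Forms spanning a boundary, days.** Main analysis: "In these cases, linear interpolation will be used to estimate the total number of days spent in each time-period". One sensitivity analysis moves everything to the most probable period. The other will "assume that all time spent hospitalised refers to the least probable time-period".
- **Forms spanning a boundary, admissions.** The main analysis places the whole stay in the likelier period. The sensitivity analysis assumes that, "where there is uncertainty about which period hospital stay occurred in, all reported hospital stay occurs in the time-period" which is least likely.
- **Protocol wording.** Footnote 3 to 17.4.2.8 reproduces the protocol's definition, which ends by excepting the initial IV days from the outcome as a whole. It says that the wording was changed for clarity.
- **Other data.** SAP 8.3 says that the Arm A treatment CRF records the duration of IV treatment for inpatients, and that diary data are combined for patients treated partly at home. No derivation in 17.4.2.7 or 17.4.2.8 refers to these records.

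**The concern.** An IV course given at the start of treatment cannot lie in T3–T15, so it may have seemed that Y_B needed no exclusion. The spanning rules change that. If a patient's first form is dated after T3, its total runs from baseline past T3. For someone treated in hospital, that total can include the initial IV stay. No rule takes the stay out before dividing or moving the total, so days whose timing is known from the treatment records are handled as days of unknown timing.

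Only Arm A has this stay. In comparisons over all patients, the literal rules therefore add T3–T15 days and stays to the IV arm and none to the oral arm. The sensitivity analyses meant to show robustness are the most exposed. The situation is foreseeable: SAP 8.9 adopts date-based allocation "Due to large numbers of visits occurring outside of appropriate visit windows".

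**Working it through.** **1. The SAP's own example.** For D days on a form at month t, with the previous visit at month p, the treatment phase receives D × (3 − p)/(t − p) and T3–T15 receives D × (t − 3)/(t − p). With D = 5, p = 2 and t = 3.5:

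- treatment phase: 5 × 1/1.5 = 3.33
- T3–T15: 5 × 0.5/1.5 = 1.67
- treatment-phase total with the 2 days already recorded: 5.33

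The SAP gives 3.3, 1.7 and 5.3, so the rule is understood correctly.

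**2. The same rule when the first form comes after T3.** A month is 28 days and T3 is week 12 (SAP 8.9). The IV course is 14 days recommended, 10 minimum (SAP 8.2). With no earlier form p = 0, so a stay of S days puts S × (w − 12)/w days into Y_B for a first form at week w.

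| First form (week) | S = 14 | S = 10 |
|---|---|---|
| 13 | 1.1 | 0.8 |
| 14 | 2.0 | 1.4 |
| 16 | 3.5 | 2.5 |
| 20 | 5.6 | 4.0 |
| 24 | 7.0 | 5.0 |

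The correct figure is 0 in every row, and it is 0 if the stay is removed before the split.

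**3. Which analyses are touched.** The treatment phase is the likelier period while 12/w > 0.5, that is, before week 24. Week 24 is a tie for which no rule is given.

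| Analysis | First form in weeks 12–24 | First form after week 24 |
|---|---|---|
| Days, main (interpolation) | part of the stay enters Y_B | part enters Y_B |
| Days, most probable | none | whole stay enters Y_B |
| Days, least probable | whole stay enters Y_B | none |
| Admission, main (most likely) | none | stay counted in Y_B |
| Admission, least likely | stay counted in Y_B | none |

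Where the table says none, the stay goes to the treatment phase, where the Y_A exclusion applies.

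**4. Order of operations.** If the total is split first and the 14 days are then taken off Y_A, a first form at week 16 gives 14 × 12/16 − 14 = −3.5 days for the treatment phase. At week 14 it gives 12 − 14 = −2.0. Removing the stay before the split is the only order that gives sensible values, but the SAP does not state it.

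**5. Illustration only.** The affected share q (Arm A patients treated in hospital with no form before T3) is not in the SAP. A simulation assumed:

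- no true difference, and 100 or 150 patients per arm
- 30% with a T3–T15 stay of 1 to 21 days
- first forms of affected patients at months 3.25 to 4.5, each with a 14-day initial stay
- interpolation, and a Mann-Whitney test over all patients (2,000 trials per setting)

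The share of Arm A with any T3–T15 stay rises by about q × (1 − 0.30): 3.5, 7 and 14 percentage points for q = 5%, 10% and 20%. The test rejects in about 7%, 14–16% and 34–48% of trials, against about 4% with q = 0.

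**The case against.** The strongest reply is that this is a missing clarification, because the intent is plain. Footnote 3 shows the protocol excepting the initial IV days from the whole outcome, and step 4 shows that a programmer who splits first gets negative values. The admission sensitivity rule is also conditioned on uncertainty about the period, and the timing of the IV course is known. Both worked examples have a previous visit at 2 months, after any initial course. This all supports removal first as the intended order. It does not supply the instruction: the exclusion is attached to Y_A alone, and the days rules act on the reported total.

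A second reply is that the follow-up form is not shown and may not count the initial stay. This stands as a condition. The Y_A exclusion would be unnecessary if the stay could never be in these data, but that is an inference.

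A third reply concerns reach, and it also stands. SAP 8.3 provides for IV treatment at home, wholly or in part, and any earlier unscheduled form shortens the interval. The statement about visits outside windows is not specific to T3 and gives no rate.

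A reader might infer that the post-treatment hospital outcomes are certain to be biased against IV. The documents do not support that. The error depends on the form's content and the programming order. Direction also depends on the summary: SAP 17.4.2.8.2 describes length of stay among patients with stays, and short interpolated fragments could lower Arm A's median there.

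**Conclusion.** The point holds on a literal reading. The rules for a form that spans T3 act on the whole reported total, the IV exclusion protects only Y_A, and the result conflicts with the protocol wording in footnote 3. For an affected patient with a 14-day stay, the main days analysis gains 2.0 spurious days at week 14 and 3.5 at week 16. The least-likely analyses gain the whole stay for first forms between weeks 12 and 24. The main admission analysis and the most-probable days analysis are touched only when the first form is after week 24.

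This assumes that the follow-up form counts the initial stay, that the patient was treated in hospital and had no earlier form, and that nobody removes the stay first. The error arises in one arm only. It adds T3–T15 days and stays to Arm A in all-patient comparisons. The overall effect cannot be sized from the SAP, and the simulated rejection rates should not be read as estimates for this trial. The outcomes are secondary, but the distortion follows from a stated rule and should be corrected before analysis.

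**What to change.** In SAP 17.4.2.7 and 17.4.2.8, state that:

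- the inpatient stay for the initial allocated IV course, with start and duration from the Treatment CRF and diaries, is removed from the days and admissions on the first follow-up form before any interpolation or most/least-likely assignment;
- this applies equally in the sensitivity analyses;
- the initial stay never contributes to Y_B.

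Confirm from the CRF completion instructions that the follow-up form counts the initial stay. If it does not, say so in the SAP, and no subtraction is needed.

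The cost is one or two sentences and a merge with treatment data already collected. For patients treated partly at home, the inpatient part comes from combining the two diaries, which SAP 8.3 already foresees. No new data are required.

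### SAP 17.4.2.7 and 17.4.2.8 allocate the same boundary-spanning hospital stay differently, and the per-period number of patients with stays in 17.4.2.8.2 is not tied to either classification

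*SAP*

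**What the plan says.** Both outcomes are reported for Baseline-T3, T3-T15 and T15-T24, and both come from visit CRFs that ask about inpatient stays since the last visit. The SAP acknowledges the difficulty, "as dates are not provided for when hospital stays take place", and handles it in two ways.

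- **Any admission (17.4.2.7).** When a key scheduled visit is missing, "the next available unscheduled/scheduled visit will act as proxy for the missing visit". For the uncertain stay itself, "we will assume that all reported hospital stay occurs in the period of interest" that is most likely. In the worked example (visits at 2 and 3.5 months, none at 3) the ruling is: "Therefore we will say that the hospital stay is more likely to have occurred in the treatment phase". Section 17.4.2.7.2 then reports "The number and percentage of participants having had at least one hospital stay during the first 3 months of treatment", and the same for the later periods.
- **Inpatient days (17.4.2.8).** When follow-up visits fall outside their window so that a CRF covers two periods, "linear interpolation will be used to estimate the total number of days spent in each time-period". The worked example has the same visits, with 5 days reported at 3.5 months and 2 days at 2 months. It gives 3.3 days to the treatment phase and 1.7 to follow-up, and a treatment-phase total of 5.3.

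Section 17.4.2.8.2 then reports, by arm and period, "The number of patients with hospital stays and their median, interquartile range and minimum and maximum total length of stay", followed by a Mann-Whitney test. Two sensitivity analyses put all the uncertain days in the most probable period (1) or the least probable period (2).

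**The concern.** Two main analyses in one report can give different answers to whether a given patient was in hospital during T3-T15. Interpolation gives a positive number of days to both periods whenever a spanning form reports any stay. If the count in 17.4.2.8.2 is simply the number of patients with more than zero days, each of them is counted twice, once in each period. Their small fractions also enter the length-of-stay summary, where they lower the minimum and can lower the median.

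The triggers differ too: a missing key visit in 17.4.2.7, an out-of-window visit in 17.4.2.8. A T3 visit that took place but was late could be accepted as it stands in one section and interpolated in the other. Within 17.4.2.7.1, the proxy sentence pulls against the most-likely-period rule. A proxy for T3 closes the treatment phase, so its form belongs to that phase even when most of the interval lies after the boundary.

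This is unlikely to be rare: SAP 8.9 reports that visits outside their windows were numerous.

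**Working it through.** **1. The SAP's own example.** Inputs from 17.4.2.8.1: 5 days reported over 3.5 - 2 = 1.5 months, boundary at 3 months, 2 earlier days.

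- Treatment phase: 5 x 1.0/1.5 = 3.33 days. Follow-up: 5 x 0.5/1.5 = 1.67 days.
- Treatment-phase total: 2 + 3.33 = 5.33 days.

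The SAP's figures reproduce. Under the 17.4.2.7 rule, which is also sensitivity analysis (1), the same patient has 2 + 5 = 7 treatment-phase days and 0 in T3-T15. The earlier 2 days make the treatment phase non-zero under either rule, so the disagreement here is about T3-T15.

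**2. How often does a stay really cross the boundary?** SAP 8.9 defines a month as 28 days, so the interval is 1.5 x 28 = 42 days with the boundary after day 28. Assumption (not in the SAP): one unbroken stay of L days, equally likely to start on any day that fits. There are 43 - L placements, of which L - 1 cross.

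| L (days) | Crosses T3 | Interpolation credits a period with no stay | Split |
|---|---|---|---|
| 1 | 0/42 = 0% | 100% | 0.67 + 0.33 |
| 5 | 4/38 = 10.5% | 89.5% | 3.33 + 1.67 |
| 7 | 6/36 = 16.7% | 83.3% | 4.67 + 2.33 |
| 14 | 13/29 = 44.8% | 55.2% | 9.33 + 4.67 |

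For L = 5, 24 of the 38 placements lie wholly in the treatment phase, 10 wholly after it, and 4 cross.

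**3. Effect on the reported percentage.** Simulation of 400,000 patients per scenario. Assumptions: true stay risk 15% in Baseline-T3 and 30% in T3-T15; off-window T3 visits 8-28 days early or late with equal probability.

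| T3 visits off-window | Interpolated, Baseline-T3 (true 15%) | Interpolated, T3-T15 (true 30%) |
|---|---|---|
| 20% | 15.8% | 31.3% |
| 40% | 16.5% | 32.5% |
| 60% | 17.3% | 34.0% |

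The most-likely-period rule gave 14.4-14.8% and 30.0-30.3%.

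**4. Effect on the length-of-stay summary.** Illustration with invented values: seven patients with 4, 5, 7, 7, 10, 12 and 14 days have a median of 7 and a minimum of 4. Adding one, three or five patients at 1.67 days gives medians of 7, 6 and 4.5, and the minimum becomes 1.67.

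**5. Effect on the Mann-Whitney test.** Assumptions: 140 patients per arm, 30% against 45% with a T3-T15 stay, stays of 2, 5, 10 or 14 days, visits every 84 days, 1,000 runs per scenario.

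| T3 visits off-window | Power, true days | Interpolated | Most probable period |
|---|---|---|---|
| 20% | 69.1% | 68.0% | 69.0% |
| 40% | 71.2% | 69.2% | 69.7% |
| 60% | 70.7% | 67.4% | 68.5% |

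The two rules differ by 1.0, 0.5 and 1.1 points. The simulation standard error is about sqrt(0.7 x 0.3/1000) = 1.4 points. With no true difference, in the treatment phase, the interpolated analysis rejected in 4.8-6.3% of runs.

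**The case against.** A Yes/No outcome cannot be split and a day total can, so different rules are not in themselves a fault. Pro-rata allocation is a reasonable estimate of total days when dates are absent. The SAP also brackets it with two sensitivity analyses, the first of which is the 17.4.2.7 rule, and gives admission its own least-likely-period analysis. This stands. It defends interpolation for a total, but not for a count of patients with stays or for a median and minimum among them. Agreement between the outcomes is restored only in a sensitivity analysis.

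It is also fair that 17.4.2.8.2 does not say where its count comes from. That it counts patients with non-zero interpolated days is the natural reading, not a stated rule.

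A reader might infer more than the SAP supports:

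- *That interpolation demonstrably places stays where there were none.* Stay dates are not collected. This is certain only for a 1-day stay; longer stays sometimes do cross. The most-likely-period rule errs too: in the 5-day example it misses a true T3-T15 stay in 14/38 = 36.8% of placements.
- *That both outcomes come from one CRF field.* Admission uses FUINPTVC and UVINPTVC; duration uses separate weeks-and-days items on the same CRFs.
- *That a form crossing the boundary by a few days is enough.* SAP 8.9 accepts assessments within 1 week of T3, and from 1 week before to 2 weeks after T15, which largely excludes such cases.
- *That the between-arm test is damaged.* The power check shows no clear difference between the rules, and nothing suggests that off-window visits differ by arm.

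**Conclusion.** The inconsistency is real and needs no assumptions: on one visit pattern the two main derivations disagree about T3-T15, and nothing in 17.4.2.8.2 links its count, or the patients it summarises, to 17.4.2.7. The consequence is a modest inflation of the per-period count and a lower minimum and median among patients with stays, expected in both arms. In the simulation the inflation is 0.8-2.3 percentage points for Baseline-T3 and 1.3-4.0 for T3-T15. Those sizes rest on assumed stay risks and off-window rates that the SAP does not give, and on the natural reading of how the count is formed. Only patients with a spanning form that reports a stay, and with no other stay in the period concerned, are affected. Bias in the treatment comparison is not shown. This is a reporting inconsistency in secondary outcomes, worth correcting because it changes a published number and costs little.

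**What to change.** 1. In 17.4.2.8.2, take the number of patients with stays in each period, and the set whose length of stay is summarised, from the 17.4.2.7 classification. The simplest way is to use sensitivity analysis (1), all days to the most probable period, for those summaries. Keep interpolated days as an alternative estimate of total days.
2. Use one trigger in both sections: no visit dated within the SAP 8.9 window for T3 or T15, so that a CRF's reporting interval spans the boundary.
3. In 17.4.2.7.1, reconcile the proxy-visit sentence with the most-likely-period rule, so that a form whose interval lies mostly after the boundary has one stated destination.
4. Check 17.4.2.15.1 and 17.4.2.16.1. Carer absenteeism borrows the same methodology through section numbers that do not exist in the SAP but appear to mean these two sections, and participant absenteeism follows it. A binary value of no absence could then sit beside a positive number of days.

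The cost is SAP wording and a change in which planned derivation feeds which table; no new data are needed. Day totals under the most-probable rule are less smooth than interpolated ones, and small mismatches may remain where the Yes/No and duration items disagree.
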